10.1.9. Publication Policy

- The results of this study may be published or presented at scientific meetings. If this is foreseen, the investigator agrees to submit all manuscripts or abstracts to the sponsor before submission. This allows the sponsor to protect proprietary information and to provide comments.
- The sponsor will comply with the requirements for publication of study results. In accordance with standard editorial and ethical practice, the sponsor will generally support publication of multicenter studies only in their entirety and not as individual site data. In this case, a coordinating investigator will be designated by mutual agreement.
- Authorship will be determined by mutual agreement and in line with International Committee of Medical Journal Editors authorship requirements.

10.2. Appendix 2: AE and SAE: Definitions and Procedures for Recording, Evaluating, Follow-up, and Reporting

10.2.1. Definition of AE

AE Definition

- An AE is any untoward medical occurrence in a clinical study participant, temporally associated with the use of a study intervention, whether or not considered related to the study intervention.
- NOTE: An AE can therefore be any unfavorable and unintended sign (including an abnormal laboratory finding), symptom, or disease (new or exacerbated) temporally associated with the use of a study intervention.

Events Meeting the AE Definition

- Any abnormal laboratory test results (hematology, clinical chemistry, or urinalysis) or other safety assessments (e.g., electrocardiogram (ECG), radiological scans, vital signs measurements), including those that worsen from baseline, considered clinically significant in the medical and scientific judgment of the investigator (i.e., not related to progression of underlying disease).
- Exacerbation of a chronic or intermittent existing condition including either an increase in frequency and/or intensity of the condition.
- New conditions detected or diagnosed after study intervention administration even though it may have been present before the start of the study.
- Signs, symptoms, or the clinical sequelae of a suspected drug-drug interaction.
- Signs, symptoms, or the clinical sequelae of a suspected overdose of either study intervention or a concomitant medication. Overdose per se will not be reported as an AE/SAE unless it is an intentional overdose taken with possible suicidal/self-harming intent. Such overdoses should be reported regardless of sequelae.

Events NOT Meeting the AE Definition

- Any abnormal safety assessments which are associated with the underlying disease, unless judged by the investigator to be more severe than expected for the participant's condition.
- The disease/disorder being studied or expected progression, signs, or symptoms of the disease/disorder being studied, unless more severe than expected for the participant's condition.
- Medical or surgical procedure (e.g., endoscopy, appendectomy): the condition that leads to the procedure is the AE.

• Situations in which an untoward medical occurrence did not occur (social and/or convenience admission to a hospital).

213033

• Anticipated day-to-day fluctuations of existing disease(s) or condition(s) present or detected at the start of the study that do not worsen.

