2.3. Benefit/Risk Assessment

2.3.1. Risk Assessment

No investigational product is used in this screening study; consequently, there are no risks due to exposure to study drug. The primary risk to patients in this protocol is the risk associated with specimen collection.

This screening protocol will include facilitation of HLA histocompatibility testing. To enable this, each patient is asked to provide a single sample of whole blood for HLA testing at the first visit following institutional standard procedure. The risks associated with this procedure are due to possible complications related to a blood draw, such as pain, bleeding and/or bruising and possible infection although serious complications are likely to be very rare. In majority of cases, this blood sample is expected to be collected with participants' routine laboratory collections that are done as part of standard of care. Therefore, the HLA blood draw may not pose additional risk.

There is a low likelihood for an additional blood draw for HLA histocompatibility testing under an investigational treatment protocol depending on how the test result was generated in the screening protocol and the requirements of the investigational treatment protocol. HLA histocompatibility genotyping test carries a low risk of false positive or false negative test results. A false positive test result will mean that the participant may be eligible to enter the screening phase of a GSK TCR T-cell investigational treatment protocol and would proceed with additional screening in the master protocol. A false negative test result would mean that the participant would not be eligible to enter the screening phase of a GSK TCR T-cell investigational treatment protocol.

The sites are directed to take all appropriate safety measures to protect the well-being of the participant and to follow-up on any SAE that would be related to the study procedure.

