6. STUDY INTERVENTION

No investigational drug will be used in Study 213033. Consequently, the following sections are not applicable to this protocol:

- Section 6.1: Study Intervention(s) Administered
- Section 6.2: Preparation/Handling/Storage/Accountability
- Section 6.3: Measures to Minimize Bias: Randomization and Blinding
- Section 6.4: Study Intervention Compliance
- Section 6.5: Treatment Overdose
- Section 6.6: Concomitant Therapy
- Section 6.7: Dose Modification
- Section 6.8: Continued Access to Study Intervention after the End of the Study

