8.4. Serious Adverse Events

The definition of an AE and SAE can be found in Appendix 2.

The investigator and any qualified designees are responsible for detecting, documenting, and reporting events that meet the definition of an SAE and remain responsible for following up SAEs that are considered related to the study procedure(s), or that caused the participant to withdraw early whether or not related to study procedures (see Section 7). AEs (SAE for this case) will be reported by the participant (or, when appropriate, by a caregiver, surrogate, or the participant's legally authorized representative).

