10.2.2. Definition of SAE

If an event is not an AE per definition above, then it cannot be an SAE even if serious conditions are met (e.g., hospitalization for signs/symptoms of the disease under study, death due to progression of disease).

A SAE is defined as any untoward medical occurrence that, at any dose:

- Results in death
- Is life-threatening

The term 'life-threatening' in the definition of 'serious' refers to an event in which the participant was at risk of death at the time of the event. It does not refer to an event, which hypothetically might have caused death, if it were more severe.

Requires inpatient hospitalization or prolongation of existing hospitalization

In general, hospitalization signifies that the participant has been detained (usually involving at least an overnight stay) at the hospital or emergency ward for observation and/or treatment that would not have been appropriate in the physician's office or outpatient setting. Complications that occur during hospitalization are AE. If a complication prolongs hospitalization or fulfills any other serious criteria, the event is serious. When in doubt as to whether "hospitalization" occurred or was necessary, the AE should be considered serious.

Hospitalization for elective treatment of a existing condition that did not worsen from baseline is not considered an AE.

Results in persistent disability/incapacity

- The term disability means a substantial disruption of a person's ability to conduct normal life functions.
- This definition is not intended to include experiences of relatively minor medical significance such as uncomplicated headache, nausea, vomiting, diarrhea, influenza, and accidental trauma (eg, sprained ankle) which may interfere with or prevent everyday life functions but do not constitute a substantial disruption.

213033

Is a congenital anomaly/birth defect

Other situations:

• Medical or scientific judgment should be exercised in deciding whether SAE reporting is appropriate in other situations such as important medical events that may not be immediately life-threatening or result in death or hospitalization but may jeopardize the participant or may require medical or surgical intervention to prevent one of the other outcomes listed in the above definition. These events should usually be considered serious.

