10.2.3. Recording and Follow-Up of AE and SAE

AE and SAE Recording

- When an AE/SAE occurs, it is the responsibility of the investigator to review all documentation (e.g. hospital progress notes, laboratory, and diagnostics reports) related to the event.
- The investigator will then record all relevant AE/SAE information in the CRF.
- It is **not** acceptable for the investigator to send photocopies of the participant's medical records to GSK in lieu of completion of the GSK /AE/SAE CRF page.
- There may be instances when copies of medical records for certain cases are requested by GSK. In this case, all participant identifiers, with the exception of the participant number, will be redacted on the copies of the medical records before submission to GSK.
- The investigator will attempt to establish a diagnosis of the event based on signs, symptoms, and/or other clinical information. Whenever possible, the diagnosis (not the individual signs/symptoms) will be documented as the AE/SAE.

Assessment of Intensity

• The Investigator will make an assessment of intensity for each AE and SAE reported during the study according to the National Cancer Institute Common Terminology Criteria for Adverse Events (NCI-CTCAE v 5.0).

Assessment of Causality

- The investigator is obligated to assess the relationship between study intervention [defined as investigational intervention and each occurrence of each AE/SAE.
- A "reasonable possibility" of a relationship conveys that there are facts, evidence, and/or arguments to suggest a causal relationship, rather than a relationship cannot be ruled out.
- The investigator will use clinical judgment to determine the relationship.
- Alternative causes, such as underlying disease(s), concomitant therapy, and other risk factors, as well as the temporal relationship of the event to study intervention administration will be considered and investigated.
- The investigator will also consult the IB and/or Product Information, for marketed products, in his/her assessment.
- For each AE/SAE, the investigator must document in the medical notes that he/she has reviewed the AE/SAE and has provided an assessment of causality.
- There may be situations in which an SAE has occurred, and the investigator has minimal information to include in the initial report to GSK. However, it is very important that the investigator always make an assessment of causality for every event before the initial transmission of the SAE data to GSK.

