4.5.3. Additional Safety Assessments

Since there is no Investigational Product administered in this study no laboratory parameters, vital signs and ECG data are collected; consequently, these safety assessments are not applicable.

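### Does the drug-trial wording of the adverse event definition in Appendix 2 undermine safety collection in a study that gives no intervention?

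*Protocol*

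**What the plan says.** Protocol 8.4 sends the investigator to the appendix: "The definition of an AE and SAE can be found in Appendix 2". There, 10.2.1 says "An AE is any untoward medical occurrence in a clinical study participant, temporally associated with the use of a study intervention", and 10.2.2 adds "If an event is not an AE per definition above, then it cannot be an SAE even if serious conditions are met". On causality, 10.2.3 says "The investigator is obligated to assess the relationship between study intervention [defined as investigational intervention and each occurrence of each AE/SAE" (the bracket is never closed), and a later bullet says "the temporal relationship of the event to study intervention administration will be considered and investigated". Section 10.2.4 describes the check on causality as a relationship to taking part in the study.

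The study has nothing to administer. Protocol 6 says "No investigational drug will be used in Study 213033", and SAP 4.5.3 opens "Since there is no Investigational Product administered in this study". Protocol 2.3.1 says "The primary risk to patients in this protocol is the risk associated with specimen collection".

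The collection rule itself is framed differently. Protocol 8.3 and 8.4.1 cover two groups from consent onward: SAEs judged related to protocol-mandated procedures, and AEs or SAEs that lead a participant to withdraw, related or not. The closing paragraphs of 10.2.2 repeat the procedure-based rule for SAEs.

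**The concern.** Taken literally, the chain runs as follows: an AE requires use of an intervention, an SAE must first be an AE, and there is no intervention. A serious complication of the blood draw would then fall outside the definition that Section 8.4 relies on, although 8.3 and 8.4.1 require it to be collected.

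Causality looks unsettled too. Three reference points appear: the intervention (10.2.3), the procedures (8.4.1 and 10.2.2) and participation (10.2.4). This could matter because, for events that do not cause withdrawal, 8.4.1 collects only SAEs judged related to a procedure, while 8.4.2 sends the reader to Appendix 2 for the method of judging. The same event could be recorded as unrelated to any intervention and related to the blood draw. At stake is consistent classification in the study's only safety assessment.

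**Working it through.** No figure in the plan depends on this, so the check is a cross-reading.

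**1. How widespread each wording is.** The term for an intervention occurs 5 times in 10.2.1 and 2 times in the causality text of 10.2.3: 5 + 2 = 7 occurrences in 2 subsections. Study procedures are the reference point in 9 places: the Synopsis, 1.3, 2.3.1, 5.4, 8.3, 8.4, 8.4.1, 8.4.3 and 10.2.2. Participation is used in 1 place, 10.2.4. Occurrences and places are different units; counted by place, it is 2 against 9. This shows which wording dominates, not the size of any effect.

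**2. What happens to each kind of event.**

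| Event | Rule in 8.3 and 8.4.1 | Literal reading of 10.2.1 with 10.2.2 |
|---|---|---|
| Serious, related to the blood draw, participant stays | Collected | Not an AE, so not an SAE |
| Serious or not, causes withdrawal | Collected, related or not | Not an AE |
| Non-serious, no withdrawal | Not collected | Not an AE |
| Serious, unrelated, no withdrawal | Not collected | Not an AE |

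The literal reading does not lose a particular class of event. It empties every row, and so voids 8.3, 8.4.1, the safety review at both visits in 1.3, and the final paragraphs of 10.2.2. A site carrying out the schedule could not work that way. The two readings part only in rows one and two, and there 8.4.1 states expressly that the event is collected.

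**3. Whether the causality question changes collection.** For withdrawal events it cannot, since they are collected regardless of cause. For other SAEs, 8.4.1 itself names what the event must be related to: a protocol-mandated procedure. Appendix 2 then supplies the manner of judging, such as reasonable possibility and alternative causes.

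**4. Whether there are really three questions.** Under 1.3, participation amounts to consent, eligibility and performance-status checks, recording of data, one blood sample, and a follow-up contact that may be by phone. Relationship to participation and relationship to procedures are in practice one question here. The remaining mismatch is procedure against intervention.

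**5. Whether it reaches an analysis.** SAP 4.5.2 summarises events by system organ class and preferred term, with listings. Protocol 9.4.1 adds tumour type and HLA subtype. Neither splits by relationship, so once an event is in the database its causality entry changes no planned table. The primary endpoint in SAP 4.2 is a count and percentage of HLA-A genotypes.

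**The case for a change.** The strongest case for acting is that relatedness decides entry for procedure-related SAEs, that 8.4.2 expressly points to Appendix 2 for assessing it, and that nothing in the documents defines the blood draw as the intervention. An investigator who followed 10.2.3 exactly could record a puncture-site complication as unrelated. The action asked for is also small: look at the causality field in the case report form and add a sentence to the synoptic report.

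The textual part of this stands. The wording does not fit the study, and the later bullet in 10.2.3 confirms it without help from the sentence with the unclosed bracket. That sentence may be incomplete, so little should be built on it. The step from wording to harm does not stand. The examples attached to the rule in 10.2.2 concern the underlying disease rather than procedure complications, and the same subsection goes on to require follow-up of procedure-related SAEs. The suggested check depends on a case report form that the documents do not include.

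Two complaints about the SAP belong elsewhere. The loose statement in SAP 4.5 about which AEs are collected does not arise from the definition in 10.2.1. A summary by relationship was never planned in the protocol.

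**Conclusion.** This is a clerical inconsistency: drug-trial template text left in an appendix to a one-sample screening study. The mention of dose in 10.2.2 and of an intervention's safety in 8.4.4 looks like the same kind of residue. It has no shown effect on event collection, on any planned safety table or on the HLA endpoint. An effect on event counts can be neither shown nor estimated, because the documents give no event rate, no actual enrolment and no case report form page.

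The conclusion assumes that sites worked from 8.3 and 8.4.1, which are specific to this study and repeated throughout. The exposure is also small: 2.3.1 expects serious complications of the draw to be very rare. SAP 1 and 5 record early closure with limited enrolment, so rewording cannot alter past collection. Anyone reusing the appendix would sensibly settle on one reference point, and the report's authors may state which causality question was asked. Neither is a change that this plan needs.

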10.2.2. Definition of SAE

If an event is not an AE per definition above, then it cannot be an SAE even if serious conditions are met (e.g., hospitalization for signs/symptoms of the disease under study, death due to progression of disease).

A SAE is defined as any untoward medical occurrence that, at any dose:

- Results in death
- Is life-threatening

The term 'life-threatening' in the definition of 'serious' refers to an event in which the participant was at risk of death at the time of the event. It does not refer to an event, which hypothetically might have caused death, if it were more severe.

Requires inpatient hospitalization or prolongation of existing hospitalization

In general, hospitalization signifies that the participant has been detained (usually involving at least an overnight stay) at the hospital or emergency ward for observation and/or treatment that would not have been appropriate in the physician's office or outpatient setting. Complications that occur during hospitalization are AE. If a complication prolongs hospitalization or fulfills any other serious criteria, the event is serious. When in doubt as to whether "hospitalization" occurred or was necessary, the AE should be considered serious.

Hospitalization for elective treatment of a existing condition that did not worsen from baseline is not considered an AE.

Results in persistent disability/incapacity

- The term disability means a substantial disruption of a person's ability to conduct normal life functions.
- This definition is not intended to include experiences of relatively minor medical significance such as uncomplicated headache, nausea, vomiting, diarrhea, influenza, and accidental trauma (eg, sprained ankle) which may interfere with or prevent everyday life functions but do not constitute a substantial disruption.

213033

Is a congenital anomaly/birth defect

Other situations:

• Medical or scientific judgment should be exercised in deciding whether SAE reporting is appropriate in other situations such as important medical events that may not be immediately life-threatening or result in death or hospitalization but may jeopardize the participant or may require medical or surgical intervention to prevent one of the other outcomes listed in the above definition. These events should usually be considered serious.

Examples of such events include invasive or malignant cancers, intensive treatment in an emergency room or at home for allergic bronchospasm, blood dyscrasias or convulsions that do not result in hospitalization, or development of drug dependency or drug abuse.

All participants will be followed for all SAEs related to study procedures and for all SAEs leading to withdrawal from the study.

The investigator and any qualified designees are responsible for detecting, documenting, and reporting events that meet the definition of an SAE and remain responsible for following up SAEs that are considered related to the study procedure(s) or that caused the participant to withdraw early, whether or not related to study procedures (see Section 7).

10.2.3. Recording and Follow-Up of AE and SAE

AE and SAE Recording

- When an AE/SAE occurs, it is the responsibility of the investigator to review all documentation (e.g. hospital progress notes, laboratory, and diagnostics reports) related to the event.
- The investigator will then record all relevant AE/SAE information in the CRF.
- It is **not** acceptable for the investigator to send photocopies of the participant's medical records to GSK in lieu of completion of the GSK /AE/SAE CRF page.
- There may be instances when copies of medical records for certain cases are requested by GSK. In this case, all participant identifiers, with the exception of the participant number, will be redacted on the copies of the medical records before submission to GSK.
- The investigator will attempt to establish a diagnosis of the event based on signs, symptoms, and/or other clinical information. Whenever possible, the diagnosis (not the individual signs/symptoms) will be documented as the AE/SAE.

Assessment of Intensity

• The Investigator will make an assessment of intensity for each AE and SAE reported during the study according to the National Cancer Institute Common Terminology Criteria for Adverse Events (NCI-CTCAE v 5.0).

Assessment of Causality

- The investigator is obligated to assess the relationship between study intervention [defined as investigational intervention and each occurrence of each AE/SAE.
- A "reasonable possibility" of a relationship conveys that there are facts, evidence, and/or arguments to suggest a causal relationship, rather than a relationship cannot be ruled out.
- The investigator will use clinical judgment to determine the relationship.
- Alternative causes, such as underlying disease(s), concomitant therapy, and other risk factors, as well as the temporal relationship of the event to study intervention administration will be considered and investigated.
- The investigator will also consult the IB and/or Product Information, for marketed products, in his/her assessment.
- For each AE/SAE, the investigator must document in the medical notes that he/she has reviewed the AE/SAE and has provided an assessment of causality.
- There may be situations in which an SAE has occurred, and the investigator has minimal information to include in the initial report to GSK. However, it is very important that the investigator always make an assessment of causality for every event before the initial transmission of the SAE data to GSK.
- The investigator may change his/her opinion of causality in light of follow-up information and send an SAE follow-up report with the updated causality assessment.
- The causality assessment is one of the criteria used when determining regulatory reporting requirements.

Follow-up of AE and SAE

- The investigator is obligated to perform or arrange for the conduct of supplemental measurements and/or evaluations as medically indicated or as requested by GSK to elucidate the nature and/or causality of the AE or SAE as fully as possible. This may include additional laboratory tests or investigations, histopathological examinations, or consultation with other health care professionals.
- If a participant dies during participation in the study or during a recognized follow-up period, the investigator will provide GSK with a copy of any postmortem findings including histopathology.
- New or updated information will be recorded in the originally completed CRF.
- The investigator will submit any updated SAE data to GSK within 24 hours of receipt of the information.

